The Marketing Authorization Holder (MAH) proposes a five-year post authorization study to be conducted in collaboration with NEAT-ID Network, a well-established network of clinical sites across Europe. This prospective observational cohort study will aim to better understand the population receiving CAB LA for PrEP in routine clinical practice, usage patterns, adherence, post marketing clinical effectiveness, discontinuations, and monitor for resistance among individuals who receive an HIV diagnosis while on CAB LA for PrEP.

Research question and Objectives:

Following the initiation of CAB LA for PrEP, the study will aim to assess usage patterns, adherence, effectiveness, safety of CAB LA for PrEP, and resistance among individuals who receive an HIV diagnosis while on CAB LA for PrEP.

The specific objectives are to:

- 1) Describe the population initiating CAB LA for PrEP, including proportion of individuals who use OLI and proportion of those with DTI
- 2) Monitor for adherence by assessing the frequency of delayed and missed injections without oral PrEP
- 3) Monitor for incidence of HIV diagnosis while on CAB for PrEP and describe the timing of incident HIV diagnoses relative to timing of CAB PrEP usage
- 4) Monitor for occurrence of drug induced liver injury (DILI) and hypersensitivity reaction (HSR) following CAB LA injections
- 5) Evaluate incidence of and risk for developing resistance among individuals with an HIV diagnosis while on CAB LA for PrEP

Study Design:

This will be a 5-year long prospective cohort study of adults and adolescents \geq 35 kg initiating CAB LA for PrEP in real-world clinical setting in the EU.

Population

HIV-negative adults and adolescents (at least 12 years of age) \geq 35 kgs initiating CAB LA for PrEP initiating OLI or CAB LA injections.

Variables

The exposure of interest in this study is use of CAB for PrEP per the approved SmPC for CAB oral and LA formulations.

Primary outcomes of interest include:

- Incident HIV diagnoses
- Proportion of individuals receiving CAB LA PrEP who receive an HIV diagnosis after 6, 12, 24, 36, and >36 months of follow-up time
- Time to incident HIV diagnoses
- ART regimen and VL testing among CAB PrEP users with prevalent and incident infections
- Adherence and Durability
- Frequency of resistance to INSTIs and specific mutations

• Frequency of DILI and HSRs following CAB OLI and CAB LA injections assessed at 6, 12, 24, 36, and >36 months

Data sources

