 - ii. Describe reasons for discontinuation of CAB LA PrEP
 - iii. Describe characteristics of the individuals who discontinue CAB LA PrEP
- 3) Effectiveness: Monitor for incidence of HIV diagnoses while on CAB for PrEP and describe the timing of incident HIV diagnoses with respect to timing of CAB for PrEP usage
 - a. Describe the proportion and number of incident HIV-1 infections while on CAB for PrEP among individuals in the following groups:
 - i. Infected during OLI
 - ii. Infected while on CAB LA: Incident HIV diagnoses, defined as HIV diagnosed after start of CAB injections while adhering to CAB LA PrEP regimen
 - b. Describe the timing of diagnosis of HIV with respect to timing of CAB for PrEP usage among individuals in the following groups:

- i. Infected during OLI
- ii. Infected while on CAB LA: Incident HIV diagnoses while adhering to CAB LA PrEP regimen
- c. Describe the proportion of incident infections among those who start with OLI and those who go to DTI separately and the timing of diagnosis of incident HIV for the overall group, and separately for the OLI and DTI groups.

The proposed study is a non-interventional study and will collect data from routine clinical practice and plans to capture all prevalent HIV-1 infections, including those captured during baseline. However, there are no plans to collect and store serum samples for subsequent testing as this is not part of standard of care.

- 4) Safety: Monitor for occurrence of DILI and HSRs following CAB LA injections
 - a. Describe the frequency of DILI after starting CAB LA at 6, 12, 24, 36, and >36 months after initiation as defined in Section 7.3.2.
 - i. Incidence proportion and rate of DILI following administration of CAB LA PrEP
 - ii. Incidence proportion and rate of CAB LA discontinuation due to DILI
 - b. Describe the frequency of HSR after starting CAB LA at 6, 12, 24, 36, and >36 months after initiation
 - i. Incidence proportion and rate of HSR following administration of CAB LA PrEP
 - ii. Incidence proportion and rate of CAB LA discontinuation due to HSR
- 5) Resistance: Evaluate incidence of and risk for developing resistance to integrase inhibitors (INSTI) among individuals in the following groups:
 - a. Incident HIV diagnoses while adhering to CAB LA for PrEP and development of resistance during treatment for HIV
 - b. CAB LA PrEP discontinued:
 - i. without subsequent oral PrEP & potential risk for HIV acquisition and viral resistance during CAB LA PK tail

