- b) Individuals with undiagnosed prevalent infections at the time of CAB PrEP initiation
- c) Durability of INSTI-based vs. non-INSTI based regimens (e.g., the numbers and proportions of those who achieve and maintain virologic suppression, the time to virologic suppression, the time to virologic breakthrough), as well as any INSTI resistance-associated substitutions that are detected upon ART failure

5) Adherence and Durability

- a) Adherence to CAB LA PrEP including OLI will be estimated from data collected via health record data
- b) Non-adherence to the dosing schedule will be assessed by:
 - Estimating the number of individuals that missed one or more consecutive injections without taking daily oral PrEP bridging while not on CAB LA injections and mean and median number of injections missed during a 6 and a 12-month period
 - Estimating the number of individuals who received the injections seven or more days later than their scheduled injection visit and median duration of delayed injections
 - Estimating the number of individuals who missed one or more consecutive injections without taking daily oral PrEP bridging or those who received the injections seven or more days later than their scheduled injection visit (Combined group a OR b) and describe characteristics for the individuals that are nonadherent
- c) Discontinuation will be defined as 2 injection cycles (~127 consecutive days) in which no injections were administered without oral PrEP bridging
- d) Describe the frequency and the regimen used for oral PrEP bridging to cover planned delayed or missed injections
- 6) Frequency of resistance to INSTIs and specific mutations among the following groups:
 - a) CAB LA PrEP started when the individual had undiagnosed HIV and subsequent emergence of resistance while on CAB monotherapy
 - b) CAB LA PrEP discontinued
 - without subsequent oral PrEP & potential risk of HIV acquistion and viral resistance during CAB LA PK tail
 - switched to oral PrEP and acquire HIV during the follow-up period and develop resistance during subsequent follow-up period while on treatment with ARVs
 - c) Incident HIV diagnosis while adhering to CAB LA for PrEP and development of resistance during treatment for HIV
- 7) Frequency of DILI and HSRs following CAB OLI and CAB LA injections assessed at 6, 12, 24, 36, and >36 months.

Hepatotoxicity related to administration of CAB for PrEP (i.e., DILI) as described below will be tabulated:

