ART regimen and VL testing among CAB PrEP users with undiagnosed prevalent infections and incident infections will be described separately, during the follow-up period. In the event of a delay of ART initiation post HIV diagnosis, the study will strive to follow the individual after ART initiation and through the end of the follow-up period. Durability of INSTI-based vs. non-INSTI based regimens (e.g., the numbers and proportions of those who achieve and maintain virologic suppression, the time to virologic breakthrough), as well as any INSTI resistance-associated substitutions that are detected upon ART failure will also be assessed and reported.

Analysis for Objective 4 (Safety: Monitor for occurrence of DILI and HSR)

Proportion and number of individuals with DILI and HSRs following CAB OLI and CAB LA injections will be shown separately at 6, 12, 24, 36 months after initiation and over the entire length of the follow-up period. Proportion and number of individuals discontinuing CAB OLI and CAB LA PrEP due to DILI or HSR will be shown at 6, 12, 24, 36 months and over the entire length of the follow-up period. Discontinuation of CAB LA PrEP or CAB OLI will be based on medical records indicating date when discontinuation decision was made by a physician and will be reviewed and confirmed by an independent adjudication committee. Frequency of hepatotoxicity and HSR events will be reported separately for OLI period and during injections.

Analysis for Objective 5 (Resistance monitoring)

Proportion and number of individuals developing drug resistance to INSTIs based on genotypic data will be assessed among the 4 different groups as follows:

a) Individuals with undiagnosed prevalent HIV, initiating CAB OLI or CAB LA PrEP, will be followed through the end of the follow-up period after ART initiation and will be monitored for resistance

- b) Individuals with incident HIV while on CAB LA PrEP will be followed through the end of the follow-up period following ART initiation and monitored for resistance
- c) Individuals who discontinue CAB LA PrEP will be followed through the end of the follow-up period and if they acquire HIV will continue to be followed after ART initiation to monitor for resistance
- d) Individuals who switch to oral PrEP and acquire HIV during the 12- month follow-up period while on oral PrEP will be followed through the end of the follow-up period after ART initiation and monitored for resistance

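### Objective 5 asks for the incidence of INSTI resistance, but the plan gives only counts and proportions in four groups without a common denominator, and no measure per CAB initiator or per person-year

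*Protocol*

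**What the plan says.** Protocol Section 6 words Objective 5 as "Evaluate incidence of and risk for developing resistance to integrase inhibitors (INSTI) among individuals in the following groups". One listed group is people who stop CAB LA "without subsequent oral PrEP & potential risk for HIV acquisition and viral resistance during CAB LA PK tail". The Synopsis is narrower: "Evaluate incidence of and risk for developing resistance among individuals with an HIV diagnosis while on CAB LA for PrEP". Section 5.2 sets the benefit of CAB against the risks of HIV acquisition and later resistance, and says the study is to quantify those risks in practice.

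Section 7.3.2 defines the outcome as "Frequency of resistance to INSTIs and specific mutations among the following groups". Section 7.6.1, which opens by stating that it gives the methods for each objective, plans: "Proportion and number of individuals developing drug resistance to INSTIs based on genotypic data will be assessed among the 4 different groups". The four groups are:

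- (a) undiagnosed prevalent HIV at initiation of OLI or CAB LA;
- (b) incident HIV while on CAB LA;
- (c) "Individuals who discontinue CAB LA PrEP will be followed through the end of the follow-up period and if they acquire HIV" (they remain followed after starting ART);
- (d) those who switch to oral PrEP and acquire HIV within a 12-month period.

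Mutations and HIV subtype are added per group. Section 6 does not require resistance testing after discontinuation and leaves the choice of tests to providers. For comparison, Objective 4 in Section 6 asks for "Incidence proportion and rate of DILI following administration of CAB LA PrEP".

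**The concern.** Section 5.2 is about the risk that a person takes on by starting CAB. A proportion among people who already have HIV does not measure that risk. It answers a different question, and with so few infections expected it answers it very imprecisely.

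If the groups also differ in denominator, overlap and leave a category out, a reader cannot safely add them up to obtain the cohort figure. A post-authorisation study could then end with a table of percentages on resistance and no usable limit on how often resistance occurs among people who start CAB.

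**Working it through.** **The plan's own precision figures.** Table 1 (Section 7.4.1) uses Clopper-Pearson limits for incident HIV. For N = 500 and 1.00%, 5/500 gives 0.3255% to 2.3181%, as printed. All 18 rows reproduce to within 0.0001 percentage points, and the five rows of Table 2 reproduce to four decimals. The protocol gives no expected count or precision for resistance.

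**Expected incident HIV cases.** Inputs are N = 500 (Section 7.4.1), at least 3 years of follow-up (Section 7.6.1), and 0.20 and 0.40 per 100 person-years on CAB in the two pivotal trials (Section 5.1). Assumptions: those rates apply here and nobody is lost.

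- Person-time: 500 × 3 = 1500 person-years.
- Cases: 1500 × 0.20/100 = 3, and 1500 × 0.40/100 = 6.
- Poisson 95% ranges: 0 to 7 at mean 3, and 2 to 11 at mean 6.
- If all 500 had 5 years: 2500 person-years, so 5 to 10 cases.

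These cases can fall only in (b), (c) or (d), because (a) is prevalent HIV by definition. The protocol gives no rate for prevalent HIV and no group sizes.

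**Precision within a group and over the cohort.** The resistant counts are assumptions. Limits are exact 95%: Clopper-Pearson for proportions, Poisson for rates. With no case, the upper limits are 1 − 0.025^(1/n) and 3.689/person-years.

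| Resistant cases | Among 3 people with HIV | Over 500 initiators | Per 100 person-years, 1500 person-years |
|---|---|---|---|
| 0 | 0% (0 to 70.8) | 0% (0 to 0.74) | 0 (0 to 0.25) |
| 1 | 33% (0.8 to 90.6) | 0.2% (0.005 to 1.11) | 0.067 (0.002 to 0.37) |
| 2 | 67% (9.4 to 99.2) | 0.4% (0.05 to 1.44) | 0.133 (0.016 to 0.48) |

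If 30% of person-time were lost (an assumption), the zero-case limit would be 3.689/1050 = 0.35 per 100 person-years.

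**Denominator of group (c).** Table 2 considers discontinuation in 2.5% to 20% of 500, which is 12.5 to 100 people. Suppose 100 discontinue, two of them acquire HIV and one has resistance. The result is 1/100 = 1% if all discontinuers are counted, or 1/2 = 50% (1.3 to 98.7) if only those with HIV are. The wording permits either.

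**Overlap and gaps.** Section 6 lists the switch to oral PrEP under discontinuation, so a person in (d) can also be in (c). Group (d) is limited to 12 months in Section 7.6.1 but runs for the remainder of follow-up in Section 6. Sections 6, 7.3.2 and 7.6.1 all name infection during OLI as a category of incident HIV. Yet (a) is prevalent HIV, (b) is incident HIV on CAB LA, and (c) and (d) begin after CAB LA is stopped or switched, so such a case has no group.

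**Genotyping.** Suppose five people have HIV, three are genotyped and one is resistant. The planned proportion could be 1/5 = 20%, which treats the two untested as not resistant, or 1/3 = 33%. Over 500 initiators the bounds are 1/500 = 0.2% and (1 + 2)/500 = 0.6%.

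**The case against.** The strongest reply is that the objective sets its own denominator. Section 6 speaks of the listed groups and the Synopsis of people with an HIV diagnosis, so a proportion developing resistance over follow-up is already an incidence proportion. This stands in part. A reader might infer that the analysis flatly contradicts its objective. It does not; the mismatch is with the wider groups in Section 6 and the stated aim in Section 5.2.

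A reader might also infer that all four groups are tiny sets of people with HIV. The protocol gives no group sizes, and (c) as worded includes discontinuers without HIV.

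Nor is it right that the cohort risk can never be obtained. Counts are reported and the number of initiators will be known, so a crude figure could be derived. It is unplanned, and overlap, the OLI gap and untested cases make it unsafe to rebuild from the group tables.

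Rates and intervals are often left to a statistical analysis plan, which is not at hand. The Objective 4 analysis paragraph also says only proportion and number, although Section 6 asks for a rate, so silence here is weak evidence that no rate will be produced. But the group definitions are fixed in the protocol, in a section that says it sets out the methods.

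Finally, one pooled rate would not show how often CAB causes resistance. Some groups cover resistance arising on later ART, which may be INSTI-based, and prevalent infections precede the first dose. This objection stands in full and shapes the fix.

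**Conclusion.** The concern holds in this form: the planned Objective 5 analysis has no common denominator, its groups are neither mutually exclusive nor complete, it does not say how ungenotyped cases are counted, and it names no measure per initiator or per person-year.

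At the target size the practical difference is large. With no resistant case, a group of three people with HIV leaves the proportion open up to 70.8%, while the cohort figure is limited to 0.74% or 0.25 per 100 person-years. These figures rest on N = 500, 3 years without loss, the cited trial rates and assumed resistant counts. The cohort limits also assume that every HIV case is genotyped. Section 7.8 expects loss to follow-up, so the real limits will be wider.

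The study tests no hypothesis and the data remain usable. This is a change worth making before the first interim report, not a fault that invalidates the study.

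**What to change.** 1. Add the number with INSTI resistance over all CAB initiators, with an exact 95% CI. For incident infections, add the rate per 100 person-years since the first CAB dose, including time after discontinuation.
2. Report cases prevalent at initiation separately, as a proportion of initiators. Separate resistance found at or near HIV diagnosis, before ART, from resistance emerging on later ART.
3. Report how many people with HIV were genotyped. Give a lower bound (genotyped resistant cases only) and an upper bound (ungenotyped HIV cases counted as resistant).
4. Make the groups mutually exclusive and complete, including infections during OLI. State the denominator of (c) and reconcile the 12-month limit in (d) with Section 6. Show group results as counts or a case listing.

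The cost is one extra table and a rewording of the groups. Section 7.5 already provides for injection dates, resistance results and follow-up after discontinuation. The drawback is that the intervals widen with loss to follow-up, and the two bounds move apart as more cases go ungenotyped.

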5.2. Rationale

The potential benefits of CAB as a new, LA PrEP regimen with superior efficacy as compared to an active comparator taken daily outweigh the potentially low risks of acquiring HIV and subsequent resistance development. There is a risk for HIV acquisition if the individual does not adhere to the CAB PrEP dosing schedule, and protective levels of CAB decrease to a level where HIV acquisition can occur. There may also be risk for HIV acquisition if the individual does not use other HIV-1 prevention strategies, including knowledge of HIV-1 status, regular testing for other sexually transmitted infections, condom use, etc. A warning and precaution are included in product labelling with recommendation that individuals should be counselled periodically to strictly adhere to the recommended CAB dosing schedule and the use of other prevention strategies. There is also a risk for the development of resistance in individuals with unrecognized or acute HIV-1 infection at the time of starting CAB PrEP.

In addition, there is risk of HIV-1 infection during or following CAB PrEP discontinuation, i.e. during the CAB exposure that is detectable >52 weeks post injection (PK tail), and subsequent emergence of CAB resistant HIV-1 strains. A warning and precaution are included in product labelling with recommendation for monitoring to clinically reassess individuals for risk of HIV acquisition and to test to confirm HIV negative status. Although not treatment limiting, CAB LA usage has the risk of hepatotoxicity and potential for HSRs. This 5-year long prospective, non-interventional study will aim to further understand and quantify the risks in real world clinical settings. The additional data generated will continue to inform clinical practice of CAB LA for PrEP usage.

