 - ii. switched to oral PrEP and acquire HIV during the remainder of the follow-up period and develop resistance during subsequent treatment with ARVs
 - c. Individuals with undiagnosed prevalent HIV at initiation of CAB PrEP and subsequent emergence of resistance while on CAB monotherapy

Resistance testing: Since this is a non-interventional study aiming to capture standard of care (SoC) in real world settings, the study will not mandate resistance testing following discontinuation of CAB LA for PrEP. Health care providers following the SmPC and applicable local guidelines will decide what laboratory and resistance tests are to be conducted while an individual is on CAB LA for PrEP. Data thus generated, including available HIV-1 subtypes, will be captured

and analysed by the study team. Resistance will also be assessed among the individuals who are non-adherent to the injection regimen and acquire HIV.

7. **RESEARCH METHODS**

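### The Objective 5 resistance groups do not carry over the protocol's own split of discontinuers, so resistance risk during the PK tail cannot be read from group (c), and group (d) uses a conflicting time window

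*Protocol*

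**What the plan says.** Protocol section 5.2 gives the reason for following people after they stop: HIV may be acquired "during the CAB exposure that is detectable >52 weeks post injection (PK tail", with emergence of CAB-resistant virus. No upper bound is given for the tail.

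Objective 5(b) in section 6 then names two subgroups of people who have discontinued CAB LA. Subgroup (i) is "without subsequent oral PrEP & potential risk for HIV acquisition and viral resistance during CAB LA PK tail". Subgroup (ii) consists of people who moved to oral PrEP, with HIV acquired at any point in what is left of follow-up and resistance arising later on ART.

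Outcome 6(b) in section 7.3.2 repeats the split as groups for reporting INSTI resistance. Its first group is "without subsequent oral PrEP & potential risk of HIV acquistion and viral resistance during CAB LA PK tail".

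Section 7.6.1, under the analysis for Objective 5, sets four groups. Group (c) is "Individuals who discontinue CAB LA PrEP will be followed through the end of the follow-up period and if they acquire HIV", after which they are followed on ART for resistance. Group (d) is "Individuals who switch to oral PrEP and acquire HIV during the 12- month follow-up period while on oral PrEP". Section 7.6.1 then has specific mutations reported within each group.

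Section 7.3.2 also gives an operational definition: "Discontinuation will be defined as 2 injection cycles (~127 consecutive days) in which no injections were administered without oral PrEP bridging".

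**The concern.** The objective asks about a specific exposure state: declining CAB levels with no other PrEP. Group (c) is defined only by having discontinued. It therefore admits people who went on to oral PrEP, and it admits HIV acquired at any interval after the last injection. Resistance during the tail is mixed with resistance arising later or on oral PrEP, and the reported proportion describes neither.

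Group (d) has a separate problem. Its window differs from that of the objective it serves, and nothing says when the 12 months begin.

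Few infections are likely to fall in these groups, so a single misplaced case could change the reported proportion. This is also the part of the study meant to describe the carry-over risk set out in the rationale.

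**Working it through.** The plan states no figure here to reproduce. The check is a comparison of texts, followed by an illustration of scale.

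**Group (c) against Objective 5(b)(i) and outcome 6(b), first group**

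| Element | Objective / outcome | Analysis group (c) |
|---|---|---|
| Oral PrEP | none after stopping | no condition |
| Time | during the PK tail | any time to end of follow-up |

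**Group (d) against Objective 5(b)(ii) and outcome 6(b), second group**

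| Element | Objective / outcome | Analysis group (d) |
|---|---|---|
| Window for HIV acquisition | remainder of follow-up (objective); follow-up period (outcome) | 12 months, start not given |
| State at acquisition | switched to oral PrEP | while on oral PrEP |

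**Are (c) and (d) disjoint?** There are two readings.

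1. Objective 5(b) and outcome 6(b) list switchers under discontinuation. A switcher who acquires HIV on oral PrEP within the 12 months then meets both (c) and (d).
2. The definition based on about 127 days requires the absence of oral PrEP bridging. If oral PrEP after a direct switch counts as bridging, the switcher has not discontinued and is not in (c). If that person acquires HIV after the 12 months, still on oral PrEP, they are not in (d) either. The protocol does not separate bridging from switching.

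Neither reading gives the two groups of Objective 5(b) cleanly.

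**Does another analysis fill the gap?** The primary effectiveness measure for Objective 3 covers HIV during OLI and during CAB LA. Time to HIV diagnosis runs from the start of CAB, not from the last injection. No analysis in section 7.6.1 is indexed to the last injection.

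**Scale (illustration).** Let F be the months of follow-up after the last injection and T the tail in months. The share of that time outside the tail is max(0, F − T)/F. Follow-up ends five years after first enrolment (section 7.2.1), so a first enrollee has F = 60 − month of last injection. T is assumed, because the protocol says only that it exceeds 52 weeks.

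| Last injection | F | T = 12 | T = 18 | T = 24 |
|---|---|---|---|---|
| Month 6 | 54 | 42/54 = 78% | 36/54 = 67% | 30/54 = 56% |
| Month 24 | 36 | 24/36 = 67% | 18/36 = 50% | 12/36 = 33% |
| Month 36 | 24 | 12/24 = 50% | 6/24 = 25% | 0% |
| Month 48 | 12 | 0% | 0% | 0% |

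A participant with only the minimum 36 months (section 7.1) whose last injection is at month 24 has F = 12, so 0% lies outside a 12-month tail. If last injections were spread evenly over 60 months, the pooled share would be ((60 − T)/60)²: 64%, 49% and 36% for T = 12, 18 and 24.

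**The case against.** The best defence is that section 7.6.1 is shorthand. Objective 5 contains four groups, 5(a), 5(b)(i), 5(b)(ii) and 5(c), and the analysis lists four. Since (d) separates the switchers, (c) may simply mean 5(b)(i). The study tests no hypothesis, injection dates and post-discontinuation resistance data are collected (section 7.5), and an SAP that is not shown could set the window.

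Much of this is fair. It rules out several stronger conclusions that a reader might draw:

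- **That the tail group appears nowhere in the plan.** Outcome 6(b) names it. The defect is that the analysis section drops it and no section gives the tail a time scale.
- **That switchers are certainly counted twice.** This depends on the reading of discontinuation.
- **That the percentages measure bias.** The plan reports proportions of individuals, and shares of follow-up time do not convert into dilution of a proportion. They are also largest for early enrollees who stop early.
- **That an infection beyond 52 weeks cannot reflect residual CAB.** The protocol's own description extends the tail past 52 weeks without limit.

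What the defence does not remove is the conflict of wording. Even if (c) is read as 5(b)(i), nothing separates early from late infections. The 12-month limit in (d) cannot be reconciled with 5(b)(ii) as written. An SAP could follow section 7.3.2 or section 7.6.1, but not both.

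**Conclusion.** The concern stands as an inconsistency between objective, outcome and analysis. Taken literally, section 7.6.1 does not deliver Objective 5(b)(i), because group (c) has neither the oral-PrEP condition nor any breakdown by time since last injection. Group (d) has an undefined 12-month window that conflicts with Objective 5(b)(ii). Membership of the two groups may overlap or leave gaps, depending on how discontinuation and bridging are read.

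The possible mixing of tail and later time ranges from none to more than three quarters of an individual's time after the last injection. That range rests on assumed tail lengths, assumed stopping times and complete follow-up. It shows that the distinction can matter but does not estimate a bias. The data can still be recovered, so this should be corrected in the protocol but does not undermine the study.

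**What to change.** Reconcile section 6 (Objective 5(b)), section 7.3.2 (outcome 6(b)) and section 7.6.1 (Objective 5, groups (c) and (d)):

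1. Define (c) as discontinued without subsequent oral PrEP and (d) as discontinued and switched to oral PrEP, with each person in only one of them.
2. State how bridging is told apart from switching for this analysis, and reconcile that with the operational definition of discontinuation.
3. Give (d) the same follow-up window as Objective 5(b)(ii).
4. Within each group, tabulate HIV diagnoses, number genotyped and INSTI mutations by bands of time since last injection at diagnosis. One band could run to 52 weeks with further bands beyond, because the tail has no stated upper bound. Give the number of discontinuers observed in each band.

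The cost is a wording change and one more table split, using dates already collected. Treatment, testing and data collection do not change. The drawback is smaller cells, some probably empty, in a table that is descriptive in any case.
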